6.4 Patient Disposition

Disposition of patients will be presented by treatment group and overall for all patients.

The number of patients included in each of the randomised, safety, ITT, and PP populations will be summarised for each treatment group and overall.

Randomised patients who discontinued from the study prematurely will also be presented with a breakdown of the reasons for discontinuation by treatment group and overall for the randomised population.

Major and minor protocol violations will be presented in the listings only.

The number of patients who need a dose reduction will be presented with means of descriptive statistics. Frequencies and percentages will be used to describe the number of subjects who took a given amount of study drug (10/20/30 mg) at each visit.

6.5 Demographic and Screening/Baseline Characteristics

The baseline demographic characteristics recorded during Screening visit (Visit 1) will be summarised by treatment group and overall by means of descriptive statistics.

The following characteristics will be provided for the Safety population:

1. Age (years)
2. Sex
3. Race (White, Black or African American, Asian, Native Hawaiian or Pacific Islander, Other)
4. Weight (kg)
5. Height (m)
6. BMI (kg/m²)
7. Vital sign – blood pressure (systolic and diastolic), heart rate, Temperature (C)
8. ECG result at Screening visit (Normal, Abnormal NCS, Abnormal CS)
9. Smoking history and current usage, if applicable

Demographic characteristics will also be summarised by site.

Prior and Concomitant medications

Medications will be coded using WHO Drug Dictionary, B3 WHO DDE-March17, using the following Anatomical Therapeutic Classification (ATC) codes;

1. Anatomical Main Group (ATC 1st level code);
2. Chemical subgroup (ATC 4th level code);
3. Preferred name.

Prior and concomitant medications will be summarised separately for safety population by anatomical main group, chemical subgroup and preferred name by treatment group.

Subjects experiencing more than one previous (or concomitant) medication within the same anatomical main group, chemical subgroup and preferred name will be counted only once.

Past disease and concomitant disease

Past disease and concomitant diseases will be coded using Medical Dictionary for regulatory activities (MedDRA) dictionary (version 20.1) and frequency distributions and percentages will be summarised by treatment group for the safety population by System Organ Class (SOC) and PT.

6.6 Compliance

Overall compliance to study treatment during the treatment period will be summarised using descriptive statistics by treatment group. Compliance will also be presented separately for jars A and B.

Total number of capsules taken from each jar and overall, as well as the treatment duration will also be summarised by treatment group.

Compliance will be analysed in the safety population.

6.7 Safety Analysis

The general objectives of this study are to establish the safety, tolerability and efficacy of litoxetine in men and women who suffer from UI. The primary analyses will focus on safety, describing the adverse events with point estimates and Clopper Pearson 95% confidence intervals. All safety analyses will be conducted on the safety population.

All AEs will be coded using the MedDRA dictionary (version 20.1).

1. Incidence and severity of Treatment Emergent Adverse Events and Treatment Emergent Adverse Events of interest (urinary retention, withdrawal symptoms) over the course of the study.

The Treatment Emergent Adverse Events (TEAEs) and the TEAEs of Interest will be summarised by treatment group. The SOCs and PTs will be used for tabulation. The number of TEAEs/TEAEs of interest and the number and the percentage of patients with at least one AE will be presented by SOC and PT for each treatment group. Within each SOC and PT, the highest severity grade attained will be reported, for AEs with divergent severities.

TEAEs/TEAEs of interest will be described with point estimates and Clopper Pearson 95% confidence intervals.

The analysis of treatment emergent adverse events is the primary safety endpoint, the analysis of TEAEs of interest is considered as part of the secondary safety analysis.

2. Treatment Emergent Adverse Events of special psychiatry interest (nervousness, anxiety, panic attacks, insomnia, aggression, mania, suicidal ideation, development/worsening of depression) over the course of the study

The Treatment Emergent Adverse Events of special psychiatry interest will be summarised by treatment group. The SOCs and PTs will be used for tabulation. The number of AEs and the number and the percentage of patients with at least one AE will be presented by SOC and PT for each treatment group. Within each SOC and PT, the highest severity grade attained will be reported, for AEs with divergent severities.

Adverse events will be described with point estimates and Clopper Pearson 95% confidence intervals.

3. Treatment Emergent Suicidal Adverse Events and Adverse Events suggestive of abuse potential

Suicidal Adverse Events and Adverse Events suggestive of abuse potential will be summarised by treatment group. The SOCs and PTs will be used for tabulation. The number of AEs and the number and the percentage of patients with at least one AE will be presented by SOC and PT for each treatment group. Within each SOC and PT, the highest severity grade attained will be reported, for AEs with divergent severities.

Adverse events will be described with point estimates and Clopper Pearson 95% confidence intervals.

4. Laboratory parameters (Haematology, chemistry, and urinalysis)

Abnormal laboratory values will be listed and their incidence, severity, and relationship to the trial drug will be tabulated by treatment. Change from baseline will be summarised by treatment. Individual changes (shift tables) and individual clinically significant abnormalities will also be presented.

While total white blood cell (WBC) count will be expressed in absolute values, differential count will be expressed as both absolute count and percentage of WBCs.

Haematology and chemistry parameters will be summarised by treatment at each visit (visit 2 and visit 6) by means of descriptive statistics. At each visit, mean of the change from baseline will be calculated by treatment group. For Electrolytes only, values at visit 3, visit 4 and visit 5 will also be summarised. In special cases, other parameters may be collected at visit 3, visit 4 and visit 5. In that case the results will be included in the summary statistics.

Shift tables presenting the number and the percentage of patients in each bivariate category (Baseline (Visit 2) versus Endpoint (Visit 6)) with regards to normal range (Low, Normal, High) will be provided for all laboratory parameters (Haematology and chemistry) by treatment group.

For liver enzymes (ALT, AST) and total bilirubin additional analysis will be performed with values expressed in ULN (upper limit of normal) in incidence tables ($>3\times$ ULN, $>5\times$ ULN, and $>10\times$ ULN for aminotransferase activities, and for total bilirubin $>2\times$ ULN).

The pregnancy test and the urinalysis will be listed only. In particular, the serum pregnancy test is performed at visit 1, visit 6 and visit 7, while the urine (dipstick) pregnancy test is performed at visit 2, visit 3, visit 4, visit 5 and visit 6. Urinalysis is performed at visit 1 and 2.

5. Absolute change from end of the Screening Placebo Run-In Period in ECG readings and Week 8. ECG parameters of interest include: ventricular rate, QT interval, corrected QT interval, PR interval, and QRS duration

Absolute values and also change from baseline (Screening Placebo Run-In Period) in ECG readings at Week 8 (Visit 6) will be summarised by descriptive statistics.

ECG parameters of interest include:

- a. Ventricular rate
- b. QT interval

- c. Corrected QT interval
- d. PR interval
- e. RR interval
- f. QRS duration.

6. Absolute change from end of the Placebo Run-In Period to each visit in standardised cuff systolic and diastolic blood pressure and radial heart rate

Absolute change from baseline (Visit 2) to each visit (Visits 3, 4, 5 and 6) for Systolic and Diastolic blood pressure will be summarised by treatment group. The average value of 3 recordings will be considered in the analysis.

A t-test will be used to test a difference between arms only for the change of systolic and diastolic blood pressure from Baseline (Visit 2) to Endpoint (Visit 6). Hypothesis testing will be carried out at the alpha = 0.05 level (two-sided) when comparing treatments. P-value and 95% Confidence Interval will be reported. Statistical significance will be declared if the rounded p-value will be less than or equal to 0.05.

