6.1.6 Physical Examinations

The Investigator or qualified designee will perform a complete physical examination at the time points outlined on the Schedule of Assessments ([Appendix 2](#)). Pre-dose abnormal findings will be reported on the medical history eCRF. Any adverse change from the baseline physical examination (Day 0 examination) will be documented on the AE eCRF. Weight will be measured at Screening, at Visit 6 (Eight weeks Postrandomization/ Early Termination Visit) and Visit 7 (Week 15, Post-Treatment Safety Follow-up Visit).

A full physical examination will include examination of general appearance, skin, neck (including thyroid), eyes, ears, nose, throat, heart, lungs, abdomen, lymph nodes, extremities, urinary system, musculoskeletal system, and nervous system, (including the central nervous system).

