7.1.7 Post-treatment Visit/End of Study Visit – Visit 7 (Day 105)

The following procedures are to be completed during the Post-treatment Visit at time points outlined on the Schedule of Assessments ([Appendix 2](#)).

- Measure and record weight
- Record current medications
- Measure and record vital signs (blood pressure, heart rate, and body temperature)
- Complete full physical examination (including weight)
- Complete the C-SSRS, BDI-II, BAI, PSQI

- Draw blood for pregnancy test in women of childbearing potential
- Draw blood for haematology and biochemistry tests (only if abnormal values were seen at Visit 6)
- Perform 12-lead ECG (only if any abnormality seen at Visit 6 represents a clinically significant worsening from baseline)
- Collect unused study drug and perform drug accountability
- Query for AEs including adverse events of special psychiatric interest

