8.7 Safety Endpoints and Analyses

8.7.1 Safety Endpoints

- Incidence and severity of AEs and Adverse Events of interest (urinary retention, withdrawal symptoms) over the course of the study.
- Adverse Events of special psychiatry interest (nervousness, anxiety, panic attacks, insomnia, aggression, mania, suicidal ideation, development/worsening of depression) over the course of the study
- Suicidal Adverse Events and Adverse Events suggestive of abuse potential will be analysed, and detailed narratives provided
- Haematology, chemistry, and urinalysis
- Actual change from end of the Screening Placebo Run-In Period in ECG readings and Week 8. ECG parameters of interest include: ventricular rate, QT interval, corrected QT interval, PR interval, and QRS duration
- Actual change from end of the Placebo Run-In Period to each visit in standardised cuff systolic and diastolic blood pressure and radial heart rate

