2.3 Primary Endpoint(s)

Safety:

1. Incidence and severity of AEs and Adverse Events of interest (urinary retention, withdrawal symptoms) over the course of the study. AEs are recorded at visits 2,3,4,5,6 and 7.
2. Adverse Events of special psychiatry interest (nervousness, anxiety, panic attacks, insomnia, aggression, mania, suicidal ideation, development/worsening of depression) over the course of the study
3. Suicidal Adverse Events and Adverse Events suggestive of abuse potential will be analysed, and detailed narratives provided
4. Lab parameters: Haematology and chemistry recorded at visit 1,2,6 and 7. Urinalysis recorded at visit 1 and 2.
5. Absolute change from end of the Screening Placebo Run-In Period in ECG readings and Week 8 (Visit 6). ECG parameters of interest include: ventricular rate, QT interval, corrected QT interval, PR interval, and QRS duration
6. Absolute change from end of the Screening Placebo Run-In Period to each visit in standardised cuff systolic and diastolic blood pressure and radial heart rate

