All AEs (excluding SAEs) will be listed, and their time to onset, frequency, severity, and relationship to the trial drug will be tabulated by treatment. Non-TEAEs will be summarised separately from TEAEs.

A subgroup analysis of TEAEs will be presented. Subjects will be divided according to age (under 65, over 65). The SOCs and PTs will be used for tabulation. The number of TEAEs and the number and the percentage of patients with at least one TEAE will be presented by SOC and PT for each treatment group and according to the patient's age.

An additional analysis will explore the TEAEs that lead to study drug reduction. Results will be presented as listings as well as with means of descriptive statistics.

Withdrawals

Premature withdrawals from the trial will be displayed and summarised by primary reason and treatment.

Physical examination

Abnormal physical examination findings will be summarised. For each physical examination a shift table presenting the number and the percentage of patients in each bivariate category (baseline versus Week 8 (Visit 6)) with regards to investigator's interpretation (Normal, Abnormal NCS, Abnormal CS, Not done) will be provided by treatment group.

The other results of targeted physical examination will be only listed.

Concomitant Medications

Concomitant medications will be presented in summary tables and listings. They will be classified according to whether they were taken before the trial (and ongoing into the trial), or started during the trial period. A medication will be defined as concomitant if taken after the date of informed consent.

The following information will be reported for each concomitant medication: generic name, route of administration, start date, stop date, frequency, dosage, and indication.

Prior Medications

Prior medications will be presented in summary tables and listings. Medications will be classified as prior medications if taken before the date of informed consent.

Vital signs

Vital signs will be summarised by treatment group at each visit (Baseline, Visit 3, Visit 4, Visit 5, Visit 6) by means of descriptive statistics and listed by subject.

Parameters collected include:

1. Heart Rate (bpm)
2. Body Temperature (Degree Centigrade)

An additional analysis will be performed also on radial heart rate. The actual change from baseline to each visit (Visit 3, Visit 4, Visit 5, Visit 6) in radial heart rate will be computed.

Past and Concomitant Diseases

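### The SAP's by-arm summaries of blood pressure and heart rate stop at Visit 6, although the primary safety endpoint covers every visit and vital signs are also taken at Visit 7

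*SAP*

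**What the plan says.** **Endpoint.** Protocol 8.7.1 lists among the safety endpoints "Actual change from end of the Placebo Run-In Period to each visit in standardised cuff systolic and diastolic blood pressure and radial heart rate". The protocol synopsis has the same item under its primary endpoints. SAP 2.3 item 6 repeats it as a primary endpoint, again "to each visit in standardised cuff systolic and diastolic blood pressure and radial heart rate". None of the three excludes a visit.

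**Collection.** The schedules in Protocol Appendix 2 and SAP Figure 1 mark vital signs at every clinic visit. For Visit 7, Protocol 7.1.7 instructs the site as follows: "Measure and record vital signs (blood pressure, heart rate, and body temperature". No condition is attached. By contrast, the Visit 7 laboratory tests and ECG are required only after abnormal findings at Visit 6.

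**Analysis.**
- SAP 6.7 item 6, blood pressure, per arm: "Absolute change from baseline (Visit 2) to each visit (Visits 3, 4, 5 and 6) for Systolic and Diastolic blood pressure will be summarised".
- SAP 6.8, heart rate change: "The actual change from baseline to each visit (Visit 3, Visit 4, Visit 5, Visit 6) in radial heart rate will be computed".
- SAP 6.8, descriptive vital signs: "Vital signs will be summarised by treatment group at each visit (Baseline, Visit 3, Visit 4, Visit 5, Visit 6"), and also "by means of descriptive statistics and listed by subject". The visits covered by that listing are not stated separately.

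**Weight.** Protocol 6.1.6 says: "Weight will be measured at Screening, at Visit 6 (Eight weeks Postrandomization/ Early Termination Visit) and Visit 7". The SAP summarises weight only as a Visit 1 characteristic in section 6.5.

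**The concern.** The SAP states the endpoint in one section and, in another, analyses it over a shorter set of visits. The heading of SAP 6.7 item 6 keeps the wording that covers all visits, and the text beneath it drops one. The change is not declared: SAP 1.5 covers nocturia, the omitted mITT population, the move from MMRM to ANCOVA and the definition of the episode endpoint, and nothing on vital signs.

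The omitted visit is also not interchangeable with the others. Visits 3 to 6 are all on treatment, and Visit 7 is the only scheduled visit off drug. If the arms differ in blood pressure or heart rate at Visit 6, Visit 7 is the only planned measurement that can show whether the difference is still there about four weeks after dosing ends. As the SAP stands, blood pressure change is tested between arms at Visit 6, and no by-arm summary then shows what follows.

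**Working it through.** The plan states no figure to reproduce here. The check compares visit lists and confirms the timing of Visit 7.

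**1. Visits collected against visits summarised**

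| Source | Post-baseline visits |
|---|---|
| Endpoint (Protocol 8.7.1, SAP 2.3 item 6) | all, none excluded |
| Vital signs scheduled (Protocol Appendix 2, SAP Figure 1) | 3, 4, 5, 6, 7 |
| Blood pressure change by arm (SAP 6.7 item 6) | 3, 4, 5, 6 |
| Heart rate change (SAP 6.8) | 3, 4, 5, 6 |
| Descriptive vital signs by arm (SAP 6.8) | 3, 4, 5, 6 |

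{3, 4, 5, 6, 7} minus {3, 4, 5, 6} leaves {7}, which is 1 of 5 visits. This counts visits. It does not measure bias or lost information.

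**2. When Visit 7 falls**

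For a subject who completes treatment, Visit 6 is Day 70, the taper lasts 7 days, and follow-up is 4 weeks (28 days) after treatment stops.

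- End of taper: 70 + 7 = Day 77.
- Visit 7: 77 + 28 = Day 105, and 105 / 7 = 15 weeks.

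Both results agree with the schedule. No vital signs are scheduled between Day 70 and Day 105, so Visit 7 is the only off-drug reading.

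**3. Does the SAP set Visit 7 aside in general?**

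No. SAP 6.8 summarises the C-SSRS, BDI-II, BAI and PSQI at Visit 7. A general rule confining summaries to the treatment period would not explain the vital-sign restriction, and the SAP offers no other reason.

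**4. Effect on tests**

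The only between-arm test in SAP 6.7 item 6 is the t-test on blood pressure change from Visit 2 to Visit 6. It does not use Visit 7, so its result is the same with or without the added summary.

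**5. Weight**

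There are two post-baseline measurements per subject who attends (Visits 6 and 7), and no SAP summary uses either. Weight is absent from the endpoint lists in the protocol synopsis, Protocol 8.7.1 and SAP 2.3.

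**The case against.** The best defence is that the primary objective concerns eight weeks of dosing, so confining vital-sign summaries to the treatment period is a reasonable choice. It would be, if declared. The endpoint as written carries no such limit, and SAP 1.5 does not introduce one.

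Four stronger readings are tempting, and the documents do not support them.

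- **A reader might infer that the Visit 7 data go unreported.** SAP 6.8 plans a by-subject listing of vital signs, which may include Visit 7. Adverse events in follow-up or after discontinuation are tabulated by arm, and withdrawal symptoms are summarised by arm with confidence intervals. What is missing is the by-arm summary of the measurements. A listing does not give a group comparison, and adverse event tables will not show mean shifts too small to be recorded as events.
- **A reader might infer that a withdrawal rebound is being missed.** Protocol 4.3 says withdrawal symptoms usually start within days of stopping and usually resolve within two weeks, although some last longer. Visit 7 is about 28 days after the taper ends. It can show persistence or recovery, but would usually be too late for an early rebound.
- **A reader might treat the unused weights as a second endpoint departure.** Weight is not an endpoint in either document, and neither promises an analysis of weight change.
- **A reader might infer that SAP 5.5 makes weight change impossible to derive**, because it sets Visit 2 as baseline for safety variables and weight is not scheduled then. But SAP 5.3, which defines those variables, does not include weight, and SAP 6.5 treats it as a Visit 1 characteristic. A Visit 1 baseline is not clearly barred.

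**Conclusion.** The point holds as an undeclared mismatch between a stated primary safety endpoint and its planned analysis. It is limited to systolic and diastolic blood pressure and heart rate, and to one of five post-baseline visits, which is the only one off drug. No hypothesis test, sample size or efficacy result is affected. The consequence is that the report would contain no planned by-arm view of whether on-treatment changes persist or resolve after dosing ends.

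This rests on two assumptions. The first is that the endpoint wording means every scheduled post-baseline clinic visit, which is its plain reading and fits the schedule. The second is that the Day 105 timing describes subjects who complete treatment and taper. Subjects who stop early are also encouraged to taper and return for Visit 7, but on a different study day. The number who will have a Visit 7 reading cannot be known in advance, given the planned 30% dropout.

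The weight data are a separate and minor matter: safety data collected without a planned summary.

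**What to change.** In SAP 6.7 item 6 and in the vital signs part of SAP 6.8, add Visit 7 to the by-arm summaries of change from Visit 2 in systolic pressure, diastolic pressure and heart rate. Use the descriptive statistics the SAP already specifies, including the number of subjects contributing, and label the row as off treatment. State that the by-subject listing includes Visit 7. The t-test at Visit 6 stays as it is, and no new test is needed.

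If the sponsor prefers to keep the summaries to the treatment period, SAP 1.5 should say so and give the reason. That would remove the silent inconsistency, but would not deliver the endpoint as written.

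Optional: add a descriptive by-arm summary of weight change from Visit 1 to Visits 6 and 7, naming Visit 1 as the baseline for weight.

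The cost is a few words in the SAP and extra rows in tables already planned, plus one short table if the weight summary is adopted. No new data are collected.
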